5.8 Recruitment and Retention

5.8.1 Recruitment

Participants will be recruited through research sites in the US and in the UK or on referral by ophthalmologists within or outside the UK or US. Members of their direct clinical care team will approach potential participants in the first instance to discuss whether they would like to consider participating. Potential participants may also contact the trial team independently. We expect to recruit up to 71 participants within a period of 48 months.

5.8.2 Retention

Participants will be supported to remain in follow-up by regular contact as per the protocol and the provision of a 24 hour hotline to a member of the trial team.

5.9 Assignment of Intervention

5.9.1 Allocation

All participants will receive the same intervention in this open label, non-randomised trial: subretinal administration of AAV2/5-hRKp.RPGR to 1 eye. The dose received by each participant will depend on the order of their enrolment in the trial according to the sequence of dose escalation, and the extent of dose-limiting events. Children will not be enrolled in the trial until the safety profile and recommended dose have been established in adults.

In the randomised expansion phase, a target of up to 48 eligible participants will be randomised in a 1:1:1 ratio to receive immediate low dose administration (n=up to 16), immediate intermediate dose administration (n=up to 16) or deferred administration (n=up to 16). Within the deferred administration treatment group, participants will be further randomised in a 1:1 ratio to deferred low dose administration (n=up to 8) or deferred intermediate dose administration (n=up to 8). The randomisation of treatment will be stratified by age at informed consent (<25 years, ≥25 years), the rationale for the stratification levels is described in Section 4.3.2.2.5 of this document. Thus, the overall randomisation ratio will be 2:2:1:1 (immediate low dose: immediate intermediate dose: deferred low dose: deferred intermediate dose).

The eye of treatment will also be randomised in a 1:1 ratio; this aspect of the randomisation is considered administrative so will not be stratified or balanced across treatment groups, the rationale for this is described in Section 5.4.2.2.2 of this document.

The randomisations will be produced by an independent statistician. The treatment and eye will be allocated in the web-based EDC system.

5.10 Data Collection, Management and Analysis

5.10.1 Data collection, management and entry

will be responsible for data management activities for the study.

Data will be captured in a fully validated, 21 CRF Part 11 compliant Electronic Data Capture (EDC) system provided by

will grant authorised site staff with access to the EDC system following system training and a successful competency assessment.

Data required by the protocol will first be recorded on source documents (e.g. medical records and study-specific data capture tools as needed) and then entered by site staff into the EDC system. All information in EDC must be traceable to these source documents. Any data recorded directly into EDC will be defined prior to the start of data collection. All data is currently anticipated to be associated with source data records.

Data validation checks will be activated during data entry to identify data discrepancies. Appropriate error messages will be displayed to allow modification or verification of data by the site staff.

Monitoring staff will review the data for completeness and accuracy, instructing site staff to make any required corrections or additions via data queries. will run further automated validation checks and review the data, raising further data queries to the sites for resolution of any inconsistencies.

The Investigator will review the eCRFs for completeness and accuracy then electronically approve the data, retaining full responsibility for its accuracy and authenticity.

Medical history and adverse events will be coded using the Medical Dictionary for Regulatory Activities (MedDRA) terminology. Prior and concomitant medication will be coded using the World Health Organization Drug (WHO)-Drug Dictionary which employs the Anatomical Therapeutic Chemical (ATC) classification system. Further coding details and data management processes will be described in a Data Management Plan (DMP).

All actions within the EDC system are captured within an audit trail. After all data have been entered, validated and signed off, the database will be locked.

At the end of the study, PDF copies of the eCRFs for each subject and supporting information will be provided to sites and the Sponsor. The electronic data will be provided to the Sponsor.

5.10.2 Non-Adherence and Non-Retention

Participants who withdraw from the trial after the intervention will be encouraged to participate in any of the planned follow-up scheduled for the trial with their consent. Data collected prior to withdrawal will be considered in the interpretation of results.

Reasons for withdrawal from the trial will be documented on a withdrawal CRF where possible, in addition to the procedures and CRF for the final visit (12 month) assessments with the participant's consent.

5.10.3 Statistical Methods

5.10.3.1 Statistical Analysis Plan

A formal Statistical Analysis Plan (SAP) will be written by the sponsor and approved by the IDMC. This trial is an open label, no crossover, phase I/II trial involving a small number of participants, and analysis of the primary and secondary outcomes will be descriptive in nature.

5.10.3.2 Statistical Methods – Outcomes

The primary outcome is safety of subretinal administration of the ATIMP defined as any of the below occurring during the 9 weeks following administration, at least possibly related to the ATIMP, not surgery alone:

- Reduction in visual acuity by 15 ETDRS letters or more
- Severe unresponsive inflammation (defined below)

- Infective endophthalmitis
- Ocular malignancy
- Grade III or above non-ocular SUSAR (see section 5.11.3)

The number of DLEs at each dose level will be summarised by cohort and overall.

Safety data relating to participants at all dose levels will allow estimation of an upper bound for the true event rate through a 95% confidence interval.

5.10.3.3 Statistical Methods – Secondary Outcome Analysis

The secondary outcomes are measures of the efficacy of the ATIMP; these will be performed on an individual participant basis and will be primarily descriptive in nature. Standard assessments will be used to measure visual function and established methods of analysis, appropriate for the assessment will be used to evaluate the data. For specialist assessments, data will be analysed by the expert team member(s) who developed the assessment. Final data will be reported descriptively.

Efficacy will be indicated by:

- 1) Slowing or halting of progressive deterioration in retinal structure or visual function that is greater than the baseline variation for that test and is sustained for at least 2 consecutive assessments.
- 2) Any improvement in visual function from baseline that is greater than the baseline variation for that test and is sustained for at least 2 consecutive assessments.
- 3) Any improvement in retinal function from baseline that is measurable by electroretinography (ERG)

Measures will be reported individually, in each dose, and aggregated across participants as the proportion who satisfy the above criteria.

Health- and vision-related quality of life (HRQoL, VRQoL) patient reported outcome and treatment experience interview data will be used to correlate a participant's feeling about their own wellbeing with clinical observations.

Any deviations from the original statistical plan will be approved by the IDMC and described in the final report, as appropriate.

5.10.3.4 Economic evaluations

No health economic evaluation is planned, but the collection of EQ5D would allow Quality Adjusted Life Years (QALYs) to be calculated.

5.11 Data Monitoring

5.11.1 Independent Data Monitoring Committee

To ensure the safety and efficacy and overall trial conduct, an Independent Data Monitoring Committee (IDMC) will be established and take part in the data monitoring. The IDMC will consist of members with specific expertise in ophthalmology and molecular genetics. The IDMC will make recommendations on the safety data prior to any dose change, and prior to the first participant aged under 16 in the UK or under 18 in the US, being dosed in the trial.

Further details of the roles and responsibilities of the IDMC, including membership, relationships with other committees, decision making processes, and the timing and frequency of interim analyses (and description of stopping rules and/or guidelines where applicable) are described in detail in the *RPGR* XLRP IDMC Charter.

5.11.2 Interim Analyses

An interim analysis may be scheduled when all patients in the immediate treatment arms (n= up to 32) of the randomised expansion phase of the trial reach 3 and 6-months post-surgery.

5.11.3 Data Monitoring for Harm

5.11.3.1 Safety reporting

will be responsible for pharmacovigilance services.

Definitions of harm of the EU Directive 2001/20/EC Article 2 based on the principles of ICH GCP apply to this trial.

Table 5: Adverse Event Definitions

Adverse Event (AE)	Any untoward medical occurrence in a clinical trial participant	
	administered a medicinal product and which does not necessarily	
	have a causal relationship with this product.	
Adverse Reaction (AR)	Any untoward and unintended response to an investigational	
	medicinal product related to any dose administered.	
Unexpected Adverse Reaction	An adverse reaction, the nature or severity of which is not	
(UAR)	consistent with the applicable product information (eg	
	Investigator's Brochure for an unauthorised product or summary	
	of product characteristics (SPC) for an authorised product.	
Serious Adverse Event (SAE) or	Any AE or AR that at any dose:	
Serious Adverse Reaction (SAR)	results in death	
	 is life threatening* 	
	 requires hospitalisation or prolongs existing 	
	hospitalisation**	
	 results in persistent or significant disability or incapacity 	
	is a congenital anomaly or birth defect	
	 or is another important medical condition*** 	
SUSAR	Suspected Unexpected Serious Adverse Reaction	

^{*} the term life threatening here refers to an event in which the participant is at risk of death at the time of the event; it does not refer to an event that might hypothetically cause death if it was more severe (e.g. a silent myocardial infarction)

- ** Hospitalisation is defined as an in-patient admission, regardless of length of stay, even if the hospitalisation is a precautionary measure for continued observation. Hospitalisation for pre-existing conditions (including elective procedures that have not worsened) do not constitute an SAE
- *** Medical judgement should be exercised in deciding whether an AE or AR is serious in other situations. Important AEs or ARs that may not be immediately life threatening or result in death or hospitalisation, but may seriously jeopardise the participant by requiring intervention to prevent one of the other outcomes listed in the table (e.g. a secondary malignancy, an allergic bronchospasm requiring intensive emergency treatment, seizures or blood dyscrasias that do not require hospitalisation, or development of drug dependency)

Adverse events include:

- an exacerbation of a pre-existing illness
- an increase in the frequency or intensity of a pre-existing episodic event or condition
- a condition (regardless of whether PRESENT prior to the start of the trial) that is DETECTED after trial drug administration. (This does not include pre-existing conditions recorded as such at baseline as they are not detected after trial drug administration)

 continuous persistent disease or a symptom present at baseline that worsens following administration of the trial treatment

Adverse events do NOT include:

- Medical or surgical procedures: the condition that leads to the procedure is the adverse event
- Pre-existing disease or a condition present before treatment that does not worsen
- Hospitalisation where no untoward or unintended response has occurred e.g. elective cosmetic surgery
- Overdose of medication without signs or symptoms

5.11.3.2 Other Notifiable Adverse Events

In order to manage the safety risks associated with administration of the vector, all safety events will be reviewed within a short time frame for all participants, as described in the trial Data Management Plan.

5.11.3.3 Procedures to follow in the event of the partners of male participants becoming pregnant

Although participants are instructed to use barrier and spermicide contraception, we cannot exclude entirely that the partner of a participant might become pregnant after administration of the ATIMP. In the unlikely event that this occurs we will notify the participant's GP that he is participating in a gene therapy trial and that, although the risks involved are minimal, there is a chance of gene transfer to the unborn child. With the participant's consent, we will contact the partner to ascertain the status of the pregnancy and the outcome. The pregnancy will be reported to on a pregnancy report form within 24 hours of the investigator becoming aware of the event.

5.11.3.4 Investigator responsibilities relating to safety reporting

The Investigator will assume overall responsibility for evaluating and reporting adverse events. In urgent situations a member of the trial team may report on their behalf, while making every effort to discuss the event with them. All non-serious AEs and ARs, whether expected or not, should be recorded in the participant's medical notes and adverse events section of the eCRF. These should be entered on to the database according to the timelines defined in the Data Management Plan to allow appropriate monitoring by the CMT. SAEs should be notified to immediately the investigator becomes aware of the event (in no circumstance should this notification take longer than 24 hours).

Clinically significant abnormalities in the results of objective tests will also be recorded as adverse events. If the results are not expected as part of disease or surgery these will also be recorded as unexpected. There are currently no expected events associated with the ATIMP.

All serious adverse events will be recorded in the hospital notes and on a paper SAE form. Adverse events will be recorded with clinical symptoms and accompanied with a simple, brief description of the event, including dates as appropriate. All adverse events will be recorded until the end of the trial (refer to Section 5.6.3 for definition), or until pregnancy outcome in the case of pregnancy if this extends beyond the end of the study. All SAEs will be recorded, fully investigated and appropriately managed until resolution or stabilisation and CI sign off.

5.11.3.4.1 Seriousness assessment

When an AE or AR occurs, the investigator responsible for the care of the participant must assess whether or not the event is serious using the definition given in Table 5: Adverse Event Definitions. If the event is classified as 'serious' then an SAE form must be completed and emailed to (or delegated body) within 24 hours.

5.11.3.4.2 Severity or grading of Adverse Events

The severity of all AEs in this trial should be graded using the toxicity gradings in NIH CTCAE Version 4.0 (NIH 2009) (Table 6: Grading of Adverse Events).

Table 6: Grading of Adverse Events

Category	Definition	
Mild (Grade I)	Asymptomatic or mild symptoms; clinical or diagnostic observations only; intervention not indicated	
Moderate (Grade II)	Minimal, local or non-invasive intervention indicated; limiting age appropriate instrumental ADL*	
Severe (Grade III)	Severe or medically significant but not immediately life threatening; hospitalisation or prolongation of hospitalisation indicated; disabling; limiting self-care ADL**	
Grade IV	Life threatening consequences; urgent intervention indicated	
Grade V	Death related to AE	

^{*} Instrumental ADL (Activities of Daily Living) refer to preparing meals, shopping for groceries or clothes, using the telephone, managing money, etc.

**Self-care ADL refer to bathing, dressing and undressing, feeding self, using the toilet, taking medications, and not bedridden.

5.11.3.4.3 Causality

Causality will be assessed in terms of both the ATIMP and the surgical procedures. Based on all available information at the time of completion of the case report form, the investigator must assess the causality of all serious events or reactions. It is of particular importance in this trial to capture and differentiate events related to:

- The ATIMP administration surgery
- The ATIMP

The differentiated causality assessments will be captured in the trial specific CRF and SAE form using the definitions in Table 7: Causality Definitions.

Table 7: Causality Definitions

Relationship	Description	Event Type
Unrelated There is no evidence of any causal relationship U		Unrelated SAE
Unlikely to be related	There is little evidence to suggest that there is a causal relationship (e.g. the event did not occur within a reasonable time after administration of the trial medication). There is another reasonable explanation for the event (e.g. the participant's clinical condition or other concomitant treatment)	Unrelated SAE
Possibly related	There is some evidence to suggest a causal relationship (e.g. because the event occurs within a reasonable time after administration of the trial medication). However, the influence of other factors may have contributed to the event (e.g. the participant's clinical condition or other concomitant treatment)	SAR
Probably related	There is evidence to suggest a causal relationship and the influence of other factors is unlikely	SAR
Definitely related	There is clear evidence to suggest a causal relationship and other possible contributing factors can be ruled out.	SAR

For each AE/SAE, a causality assessment for the ATIMP administration surgery must also be provided. Any events related to the surgery alone will not be reported to the relevant regulatory agencies.

5.11.3.4.4 Expectedness

In view of the very limited clinical experience with the ATIMP there are at present no events considered as expected for the ATIMP. Therefore, any SAEs that are related to the ATIMP (i.e., considered a SAR) will be deemed a SUSAR (suspected, unexpected, serious adverse reaction) and MHRA, REC/IBC, FDA, and NIH reporting guidelines apply (see Notifications sections of the protocol).

Table 8: Assessment of expectedness

Category	Definition
Expected	An adverse event that is classed in nature as serious and which is consistent with the information about the surgery listed in the Investigator Brochure or clearly defined in the protocol. In view of the very limited clinical experience with the ATIMP there are at present no events considered as expected for the ATIMP listed in the current Investigator Brochure.
Unexpected	An adverse event that is classed in nature as serious and which is not consistent with the information about the ATIMP and surgery listed in the Investigator Brochure* or clearly defined in the protocol.

^{*}This includes listed events that are more frequently reported or more severe than previously reported

The reference document to be used to assess expectedness against the ATIMP and surgery is the Investigator Brochure. Procedure-related adverse events cannot be considered attributable to the ATIMP.

Previous experience with AAV-mediated gene therapy in the retina indicates that the risks are largely limited to the eye. A temporary and/or mild decrease in visual acuity, due to detachment of the retina or post-surgical inflammation, is to be expected after intraocular surgery and will not cause undue discomfort to the participants. Therefore, we have defined the success criteria for the primary outcome for safety as the absence of an adverse event that has a substantial and sustained negative impact on vision, as well as the absence of any non-ocular SUSAR.

Expected events associated with surgery:

- Temporary and/or mild decrease in visual acuity (to hand movements or better for a period of up to 8 weeks), due to detachment of the retina or post-surgical inflammation
- Ocular discomfort

- Epiphora
- Periocular swelling
- Diplopia
- Ptosis
- Subconjunctival or intraocular haemorrhage
- Corneal abrasion
- Retinal tear or detachment
- Wound leak
- Ocular hypotony or raised intraocular pressure
- Overfill or underfill of any intraocular gas tamponade
- Mild intra- or extra-ocular inflammation
- Scleral or conjunctival suture granuloma
- Lens opacity or dislocation
- Systemic adverse events related to sedation or general anaesthesia, including nerve or vascular injury

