4.1.5.5 Risk of surgical adverse effects

The risk of significant surgical adverse effects is similar to the standard surgical care for other common forms of vitreo-retinal disorders, including bleeding in the eye, infection and increased pressure inside the eye. To manage the risk of surgical adverse events, only highly experienced surgeons will perform the procedure. Complications of surgery are typically managed effectively by medication or further surgical intervention, but can rarely result in lasting harm to sight. The risk of lasting severe impairment of sight from vitrectomy surgery is approximately 1 in 1000. We have identified some reduction in outer retinal thickness and deterioration in acuity in 2 of the 12 participants in our previous clinical trial of gene therapy for LCA RPE65, believed to result from temporary retinal detachment which is a deliberate consequence of targeted administration of the vector suspension, but no other significant surgical adverse effects.

Delivery of ATIMP to the subretinal space will be performed by standard surgical vitrectomy. This will involve a 3-port pars plana vitrectomy followed by injection of ATIMP using a fine cannula through small retinotomies, resulting in a temporary retinal detachment. Previous gene therapy clinical trials have shown that the bleb of subretinal ATIMP suspension can be expected to resolve spontaneously over the course of the first 24 to 48 hours postoperatively as the fluid is absorbed by the underlying retinal pigment epithelium.

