4.3.2.1 Dose Escalation Criteria and Dose Limiting Events

Dose escalation will be undertaken in adults, based on an escalation rule around dose-limiting events (DLEs). An IDMC will review data from a minimum of 9 weeks of follow up from each cohort of 3 participants, before recommending the next dose to be assessed in a further cohort of patients.

A DLE is defined as any of the below occurring during the 9 weeks following administration, at least possibly related to the ATIMP, not surgery alone:

- Reduction in visual acuity by 15 ETDRS letters or more
- Severe unresponsive inflammation (defined below)
- Infective endophthalmitis
- Ocular malignancy
- Grade III or above non-ocular SUSAR (see section 5.11.3)

Severe unresponsive inflammation will be defined according to the Standardisation of Uveitis Nomenclature (SUN) Working Group grading system (Jabs *et Al.* 2005) i.e.

- anterior chamber cells 3+ (26-50 cells in a field size of 1mm x 1-mm slit-beam), or
- anterior chamber flare 3+ (marked, iris and lens details hazy), or
- vitreous haze 3+ (Ophthalmology 1985; 92:467-71)

that fails to improve by 2 steps (or to grade 0) during a 6 week period.

Review of safety data will be undertaken by the IDMC prior to each dose escalation. Children will be included at up to the highest safe anticipated therapeutic ATIMP dose recommended by the IDMC, once a safety profile has been established in adult participants.

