1.3. Statistical Hypotheses for Trial Objectives

1.3.1. Primary Safety Hypothesis

The objective of the dose escalation phase is to estimate the proportion of subjects who experienced the primary safety outcome. No formal hypothesis testing will be conducted.

The primary safety outcome is defined as any of the events delineated below and occurring during the 9 weeks following administration, at least possibly related to the ATIMP, not the surgery alone:

- Reduction in visual acuity by 15 Early Treatment Diabetic Retinopathy Study (ETDRS) letters or more
- Severe unresponsive inflammation (defined in Section 4.2.1 of the protocol)
- Infective endophthalmitis
- Ocular malignancy
- Grade III or above non-ocular suspected unexpected serious adverse reaction (SUSAR) (Protocol MGT009, Section 5.11.3.4.2 Severity or Grading of Adverse Events).

Safety will be assessed for 12 months following ATIMP administration for immediate treatment participants in this study (Protocol MGT009) by study phases (dose escalation, dose confirmation and expansion phases) and overall, comparing with 6 months data in deferred treatment arm prior to treatment. Safety outcome captured in a separate long-term follow-up study (Protocol MGT010) for a further 4 years will be summarized separately.

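### Protocol 5.11.3.4.4 bars any procedure-related event from ATIMP attribution, contradicting the DLE, primary safety and causality rules, which exclude only events due to surgery alone

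*Protocol*

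**What the plan says.** The rule in question is in Protocol 5.11.3.4.4 (Expectedness): "Procedure-related adverse events cannot be considered attributable to the ATIMP". It carries no qualifier. The same section states that no event is at present expected for the ATIMP, so every serious event judged ATIMP-related becomes a SUSAR.

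The outcome definitions use a different test. Protocol 4.3.2.1 defines a DLE as a listed event within 9 weeks that is "at least possibly related to the ATIMP, not surgery alone". Protocol 5.5.1 and 5.10.3.2 use the same condition for the primary safety outcome, and SAP 1.3.1 repeats it: "at least possibly related to the ATIMP, not the surgery alone".

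The rating rules are in Protocol 5.11.3.4.3 (Causality): "Causality will be assessed in terms of both the ATIMP and the surgical procedures", and "For each AE/SAE, a causality assessment for the ATIMP administration surgery must also be provided". Table 7 there classes an event as a serious adverse reaction from the level of possibly related upwards. At that level it accepts that other factors may have contributed. On reporting, the section says: "Any events related to the surgery alone will not be reported to the relevant regulatory agencies".

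**The concern.** The ATIMP reaches the eye only through vitrectomy and a deliberate, temporary retinal detachment (Protocol 4.1.5.5 and 5.4.1.5), so its effects and those of the surgery can be hard to separate. The protocol itself gives both causes for one kind of event. Protocol 4.1.5.1 treats early intraocular inflammation as a vector risk, and 4.1.5.5 lists persistent postoperative inflammation among the complications of the surgery. Severe unresponsive inflammation is a component of the primary outcome.

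If two sites rate such an event as possibly related to both causes, one following the outcome definitions counts it and one following the Expectedness sentence does not. The attribution rule decides what enters the primary safety proportion. It also decides which serious events are reported as SUSARs and, through the non-ocular SUSAR component, feeds back into the primary outcome. I found no statement of which section prevails, and the trial runs at several centres in two countries.

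**Working it through.** The plan states no figure to reproduce, so the check is textual. Each event gets two ratings, giving four combinations:

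| ATIMP rating | Surgery rating | Under 4.3.2.1, 5.5.1, 5.10.3.2, 5.11.3.4.3 and SAP 1.3.1 | Under 5.11.3.4.4 read literally |
|---|---|---|---|
| At least possible | Unlikely or unrelated | ATIMP-related | ATIMP-related |
| At least possible | At least possible | ATIMP-related | Barred |
| Unlikely or unrelated | At least possible | Not ATIMP-related | Not ATIMP-related |
| Unlikely or unrelated | Unlikely or unrelated | Not ATIMP-related | Not ATIMP-related |

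1. The two readings differ in the second row only. An event there is at least possibly due to the ATIMP and so is not due to surgery alone. It counts in the primary outcome if it meets a listed criterion, and it is a SUSAR if serious. The literal sentence removes it from both.
2. No row moves the other way, so an error from applying the sentence can only lower the attributed count.
3. The number of events in the second row is not given anywhere, so the total effect cannot be calculated.
4. The effect of one such event follows from the planned maxima. The immediate low-dose and intermediate-dose arms have up to 16 participants each. Escalation, paediatric confirmation and immediate expansion together have up to 18 + 5 + 32 = 55. One reclassified participant changes the proportion by:
   - 1/16 = 6.25 percentage points in one immediate-dose arm
   - 1/32 = 3.1 points in the pooled immediate arms
   - 1/55 = 1.8 points across all those treated outside the deferred arm
5. For DLEs, Protocol 4.3.2.2.4 stops escalation when at least 2 of 3 to 6 participants have one. Moving one of two events in a cohort of 6 would change 2/6 (33.3%) to 1/6 (16.7%) and undo the stop. This is illustration only, because Protocol 4.3.2.2.5 says adult escalation is complete.
6. The planned SAP outputs would not clearly expose the problem. SAP 6.1 tabulates relationship to ATIMP and relationship to surgery separately, and two separate tables do not show how many events carry both. The listing in SAP Section 6 covers events already classed as primary safety outcomes, so an event dropped at classification would not appear in it.

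**The case against.** The strongest reply is that the sentence is shorthand for surgery-alone events and sits in a section on expectedness, while the sections that govern causality and define the outcomes all keep events with both causes. The SAP does not adopt the sentence, and all adverse events are still recorded and tabulated. Much of this stands: a reader might infer that such events are lost from the primary result, but the documents do not show that. Loss requires a site or the sponsor to let this sentence override the rest. The reply does not remove the contradiction, because the sentence has no limiting word and stands in the section that sets the SUSAR rule.

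Two further inferences are tempting and not supported:

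- **Projecting a count from the previous trial.** Protocol 4.1.5.5 reports "deterioration in acuity in 2 of the 12 participants" in a previous gene therapy trial. Applied to 55 participants, 55 × 2/12 = 9.2 events. But that was a different product, and the text does not say that the losses reached 15 letters or fell within 9 weeks. It puts them down to the detachment made for delivery. Events attributed to the procedure alone are excluded under both readings and would not move.
- **Reading the surgical list as a filter.** Protocol 5.11.3.4.4 lists as expected after surgery: "Temporary and/or mild decrease in visual acuity (to hand movements or better for a period of up to 8 weeks". Eight weeks is most of the 9-week window, so a reader might think the list empties the acuity component. It does not. That component has no expectedness condition, and expectedness enters the primary outcome only through the non-ocular SUSAR component.

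One limit also stands. The SAP cites protocol v12.0, while the amendment table in the protocol reviewed ends at v11.0. Whether the sentence survives in v12.0 cannot be seen.

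**Conclusion.** The point holds as a contradiction in the text. Followed literally, the sentence in Protocol 5.11.3.4.4 gives a result opposite to the DLE definition, the primary safety outcome in both documents and the causality rules, for exactly one class of event: those rated at least possibly related to both the ATIMP and the surgery. The consequence is a risk of inconsistent classification, with possible under-counting in the primary safety proportion and under-reporting of SUSARs. Actual loss of events is not established.

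The total size is unknown; the per-event shifts above assume that the planned maxima are reached. Completed adult escalation decisions cannot be altered by correcting the wording. The conclusion also assumes that the sentence still stands in the protocol version that governs the analysis.

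**What to change.** Reconcile Protocol 5.11.3.4.4 with 4.3.2.1, 5.5.1, 5.10.3.2, 5.11.3.4.3 and SAP 1.3.1 by limiting the sentence to events related to the procedure alone. State that an event rated at least possibly related to the ATIMP is ATIMP-related for the DLE, the primary safety outcome and SUSAR reporting, even if it is also rated as related to surgery. If v12.0 has already made this change, nothing further is needed in the protocol.

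Optionally, add to SAP Section 6 a table of all events that meet a component criterion, whatever their attribution, cross-classified by ATIMP and surgery rating. Including unattributed events matters, because a site that applied the literal sentence when rating would have recorded surgery only.

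The cost is one sentence in the protocol and, if wanted, one table from ratings the CRF already captures. The downside is that the attributed event rate may look slightly less favourable.
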